#### Global Outcome

- Glasgow Outcome Scale Extended (GOS-E) A revision of the GOS, a commonly used global outcome measure in TBI studies; a core NINDS CDE. This test will not be administered during telehealth visits.

#### Cognitive and TBI Symptom Severity

- Rivermead Post Concussive Symptom Questionnaire (RPQ) will be used to measure postconcussive symptoms (PCS); a core NINDS CDE. This test will not be administered during telehealth visits.
- Structured Interview for Collecting Head Trauma Event Characteristics (DoD HTEC), head trauma history and to assess eligibility.
- The Neurobehavioral Symptom Inventory (NSI) a PCS measure mandated for use in the VA, and is a NINDS TBI supplemental CDE recommended for use in Military studies.

#### Cognitive Compensation

- Memory Compensation Questionnaire (MCQ). Rates the extent to which patients use various strategies to improve memory performance. This test will not be administered during telehealth visits.

#### Cognitive Functioning (all tests were selected because of their excellent validity and reliability, and the availability of large normative databases)

- The Wide Range Achievement Test-4 (WRAT-4) Baseline ability, a NINDS supplemental TBI CDE.
- Hopkins Verbal Memory Test-Revised (HVLT-R) A measure of verbal list learning and delayed recall.
- Wechsler Adult Intelligence Scale-4th Edition, Digit Span Subtest (WAIS-IV) A WAIS-IV subtest that measures attention and working memory, and is a NINDS supplemental TBI CDE.
- Wechsler Adult Intelligence Scale-3rd Edition, Symbol Search Subtest (WAIS-III) WAIS-III subtest measuring processing speed; component of WAIS PSI, a core NINDS TBI CDE. This test will not be administered during telehealth visits.
- Trail Making Test (TMT) DKEFS- trails subtest is a visual-motor task used to measure flexibility in thinking (executive function) and processing speed, a core NINDS TBI CDE. This test will not be administered during telehealth visits.
- Controlled Oral Word Association Test (COWAT) Verbal fluency, a supplemental NINDS TBI CDE.

#### Depression:

- Beck Depression Inventory-II (BDI-II) A widely used 21-item measure of current levels of depression.

#### Psychiatric Disorders:

- Mini-international Neuropsychiatric Interview – Depression, Substance Use Disorders, Manic Episode, Hypomanic Episode, and Psychotic Disorders subtests (MINI) Brief structured interview for the major Axis I psychiatric [DSM-V version will be substituted if available at the time of funding].

- Brief Symptom Inventory 18 (BSI 18) Psychological symptom complaints; a core NINDS CDE. This test will not be administered during telehealth visits.

Cognitive Related Functional Impairment:

- Neuro-QOL. Health-related quality of life assessment tool; a NINDS supplemental TBI CDE. This test will not be administered during telehealth visits.

Social Role Participation:

- Craig Handicap Assessment Reporting Technique - Short Form (CHART-SF) Consisting of 6 subscales; a NINDS core TBI CDE. This test will not be administered during telehealth visits.

General Functioning:

- Sheehan Disability Scale (ShDS). A brief self-report measure of functional impairment. This test will not be administered during telehealth visits.

Quality of Life:

- Satisfaction with Life Scale (SLS) A 5-item measure assessing global life satisfaction or quality of life.

Participant Satisfaction:

- The Client Satisfaction Questionnaire (CSQ-8) A questionnaire used routinely in the Seattle Post Deployment Health Services and PTSD Clinic to assess satisfaction with care.

Other Measures:

- Severity of Dependence Scale (SDS) A 5-item measure assessing severity of substance dependence. This test will not be administered during telehealth visits.
- Scale for Suicide Ideation (SSI), a 21-item interviewer-administered rating scale that measures the frequency and severity of suicidal ideation. This test will not be administered during telehealth visits.
- Functional Outcomes of Sleep Questionnaire (FOSQ-10) A 10-item measure of sleep function.
- Insomnia Severity Index (ISI) A 7-item measure of insomnia severity. This test will not be administered during telehealth visits.

Scheduling of Assessment Measures: Assessment measures are administered at times indicated in Table 3.

**Table 3: Visit and Assessment Schedule (updated for telehealth visits)**

	Visit 1, Wk. 0	Visits 2-6	Visit 7, Wk. 7	Visits 8-12	Visit 13, Wk. 14
Duration	180 mins	90 mins	60 mins	90 mins	180 mins
Purpose	screen + baseline	intervention	mid-assessment	intervention	post-assessment
Informed Consent	x				
Demographic	x				
CAPS-V	x				x
PCL-5	x		x		x
DoD HTEC	x				
NSI	x		x		x
BDI-II	x		x		x
MINI – M,H,&P	x				
MINI – MDD & SUD	x				
SLS	x		x		x
CSQ					x
NP Battery	x				x

## 5.6 Data Analysis

### Statistical Analysis of Data

**Data integrity.** Data will be collected at both participating sites: Portland VA and VA Puget Sound. The co-PIs and multi-site project coordinator will be located at the Portland VA. Trained study personnel will conduct the structured clinical screening interview. Similarly, a paper questionnaire will be used to guide the medical record review to ensure that the same historical information is gathered and coded for all subjects. The self-report questionnaires/surveys and psychological and cognitive assessment battery consists of standardized protocols with specific/scripted questions and scoring systems that quantify answers. All study personnel from all study sites who will be gathering data from these sources will be trained by the co-PIs regarding the collection of data and will have professional education and training as required for these instruments.

Data will be labeled with a code unique to each patient. All hard copy data will be stored in locked filing cabinets in locked rooms, while electronic data will be stored in password-protected files in a limited access folder on the secure VA network drive. Each study site will maintain a key code that links that site's patients with their coded identifier with key code stored separately from all other study data. Only the multisite and site PI's and the multisite and site study coordinators and research assistants will have access to the key code linking document. Materials with protected health information will be stored in separate locked file cabinets from coded materials to ensure privacy. Special multilevel data security programs have been written into the network operating system to ensure that only authorized research personnel have access to the Center Network. Backups of daily changes are done regularly and all other data are backed up on a rotating schedule. An electronic archive of all data is kept offsite to insure against loss by fire, theft, etc. All statistical transfer routines are inherently secure via operating platform and contain no patient names or personal data.

A database will be developed using Microsoft Access or Excel by the multi-site study team located at the Portland VA, and adapted from the current Merit study. The database will be tested and the final version will be distributed to participating study sites by the Portland VA data manager. Two study support persons located at each site will enter data from the hard copy forms into the database to ensure accuracy of data entry. All data entry discrepancies will be solved by the site study coordinator. Hard copy source documents will be kept and stored at the VA site location (Portland or VA Puget Sound) at which they were gathered; data collected at the American Lake Division will be transported securely to the Seattle Division for storage. For adherence monitoring, digital audio-recordings of sessions will be kept in limited access drive on the VA network. The recording will be coded, password-protected and encrypted. Following completion of the planned analyses, the statistician's files will be sent back to the VA site to be stored with all other data and subject to all IRB-approved storage and deletion procedures. The statistician will be able to retain a data dictionary and all associated syntax and output files, provided that these files do not contain any identifiable data. Throughout the entire course of the study, the off-site statistician will only ever have access to coded data. Additionally, the off-site statistician holds a VA appointment with the San Diego VA and will only analyze and maintain databases from within the VA network.

**DATA ENTRY FLOW:** The following sequence of events will be followed: 1) Assessment forms completed by clinical rater; 2) Forms reviewed by rater and data manager for completeness; 3) Assessment forms entered into database; 4) Data entry procedures verify key items, out of range and unacceptable values; 5) Data

added to database; 6) Programs run to check for missing data and for logic errors; 7) Data reviewed by investigators, clinical staff, and key data management personnel at regular protocol review meeting for final validity.

**DATA SAFETY MONITORING:** Safety monitoring analyses will occur every six months from study inception through completion. The unblinded data manager will provide the blinded study statistician with a limited data set containing blinded group membership data, i.e., group membership that is numerically labeled but unidentifiable as treatment vs. control group. This dataset will also contain in-progress data safety variables including CAPS scores and any serious adverse events including 1) the onset of imminent risk of harm to self or others such as active thoughts of suicide or violence with expressed plan and intent to act; 2) the onset of psychotic and or manic symptoms; 3) a decline in global daily functioning indicating that inpatient mental health services are required for stabilization; 4) the onset or exacerbation of major medical illness that interferes with participation in regular outpatient mental health services. Differences between the treatment and control groups will be analyzed using t-test comparisons. We will consult with the CIRB and consider the appropriateness of study suspension if, at the set data monitoring time periods every six months, we find that either group of participants is experiencing, on average, an increase in CAPS scores of 12 or more points and/or is experiencing, on average significantly more SAE's including those defined above. For serious adverse events, significance is defined as a statistically significant difference of  $p < .01$  and/or a large effect size equivalent to a Cohen's  $d$  value of .8 or greater. The two study PIs will be responsible for notifying and consulting the CIRB of any conditions meeting criteria for possible study suspension within one business day of discovery.

Randomization procedures as well as overall multisite study interim, data safety monitoring and final data analyses will be conducted by our contracted statistician, [name] who is affiliated with University of California, San Diego. [name] will receive a limited data set copied in encrypted format onto CD's sent via secure FedEx with tracking services. This data set will be considered a limited data set due to inclusion of patient assessment dates and otherwise is de-identified. A Data Use Agreement will be pursued between the VAPORHCS and [name] recognizing the agreement of the terms for use of this data which shall be transmitted and accessed strictly for data analysis purposes pursuant to the goals of this study.

**Sample size and power.** Power analyses are performed for primary hypotheses *1a, 1b and 2a*, incorporating the longitudinal nature of the design. We propose a Random Regression model (also known as Multilevel or Growth Curve Models) as a basis of the analysis. In this approach, the repeated measures over time for each individual subject form a trajectory that can be described by a relatively simple model with a few parameters, here a linear model described by intercept (baseline value) and slope (rate of change). With random assignment to groups, there should be no group differences in baseline values, and slopes differences reflect treatment effects. With repeated measures, repeated observations within subjects are potentially correlated, impacting tests of significance. When within subject correlation is properly incorporated, the repeated measures analysis takes full advantage of all information obtained from each subject, thereby greatly increasing statistical power over cross-sectional methods. This approach can model differential patterns over repeated assessments instead of totals at one point and therefore increases the reliability of the measurement of response (since the slope combines repeated measures which cancel much of the error of measurement), and increases the protection against the major effects of missing data (since one can impute from the non-missing data for that subject as well as for other similar subjects). These result in increased power to detect effects and precision of effect size estimation without increased sample size.

Power calculations can be made for repeated measures designs under specified assumptions. Hedeker et al. extend Diggle et al.'s method for various covariance structures. Procedures described by Hedeker et al. for Random Regression Models were used for the proposed study to estimate needed sample size using RMASS (see Hedeker <http://tigger.uic.edu/~hedeker/ml.html>). Data from our previous studies were used to calculate effect sizes. The design consists of a 2 (sites) X 2 (CABA vs TAU) X 4 (baseline, 7, and 14 weeks) where the slope is the dependent measure. Site and Treatment by Site interaction were included as "nuisance parameters", that is, included to account for possible overall site effects (Site) or possible site differences in treatment effects (Treatments X Site). With a balanced design (equal numbers at each site in each group), ignoring these would not increase the probability of Type I error, but would increase the Error Sum of Squares (SS) and probability of Type II error. The main effect of treatment represents the common effect size across sites if there is one, or the average site effect, if there is heterogeneity across sites. This is true because sample sizes will be balanced across treatment groups and sites. In any case, the analysis procedures will include site and site interaction effects to avoid allowing site effects to bias treatment comparisons. However, if we detect imbalances between the treatment groups within each site, we will follow the primary analyses with subsequent analyses considering the imbalances to verify that conclusions are not affected by imbalances.

Other assumptions needed are number of repeated measures, alpha-level, nature of the hypothesis (one- or two-sided), drop-out rate, and variance-covariance matrix of the longitudinal data. We assume an overall Type-I error levels alpha of .01 to .02, drop-out rate of 15%, and autoregressive covariance structure, with correlation between sequential assessments set at 0.45. Autoregressive covariance structures assume points closer together in time are more correlated than points further in time, which is more plausible compared to the equal correlation between all pair of assessments regardless of time separation assumed by the compound symmetry design. *When multiple analyses are conducted for a given hypothesis, Type I error rates will be controlled*

*by a Westfall-Young procedure, we would include an alpha level of .04 for Hypothesis 1a, .03 for Hypothesis 1b and 2a, and .05 for Hypothesis 2b.* We estimate that with the proposed sample size of 192 (15% drop-out) patients (96 for each of the two groups), the study will have minimum power of 80% to yield a statistically significant result for a medium effect size. Hedker et al. defined medium effect size in this model as a between-group difference increasing linearly from 0 at baseline to .5 SD units at the last time point. Hypothesis 2b is a cross-sectional hypothesis using data collected only in the week 14 of the study. The proposed sample size will provided us with a minimum power of 90% to detect a medium to large effect size. The former and foundational Behavioral Activation for PTSD study by [name] and [name] yielded the following rates which also informed our proposed sample size determination: 192 screened, 81 enrolled, 10 dropped (12.3% dropout rate), 101 screen failures.

**Outcome analyses:** Data analyses will proceed in stages. Descriptive statistics and exploratory graphing such as frequencies, means, standard deviations, stem and leaf diagrams, and scatterplots will be used to assess normality of data in terms of presence of skew and/or outliers. Continuous outcome data will be transformed if necessary using an appropriate transformation such as the log transform for skewed long tailed data. Prior experience with this kind of data leads us to expect that for all variables, the distributions will be skewed and the variances not homogeneous. Similarly, potential covariates will be summarized with descriptive statistics and graphs to determine the most appropriate way to treat these variables (e.g., continuous, categorical, or interval representation). For outcome measures acquired at baseline, 7, and 14 weeks, the analytical approach will address the nature of the outcome, as well as accommodate the within

individual variability due to the repeated assessments. Results from will be inspected for bias due to drop-outs or missing data.

For major analyses of central hypotheses (1a-1b and 2a), we propose to use Mixed Effects modeling to account for clustered data (i.e., repeated assessments within individuals, treatment groups, and sites). The mixed effects approach provides more information and more power compared to cross-sectional analyses which focus on analysis of one summary index or time-until event methods and traditional analytic approaches such as a change score, end-point or repeated measures analysis of variance (ANOVA). This method allows inclusion of subjects with missing data or those who were terminated early in the study, without relying on data imputation procedures. Two specific forms of the Mixed effects model strategy are commonly implemented: random regression models, or hierarchical models (HLM) or multilevel models; and mixed model analysis of variance (MMANOVA). Each outcome variable will be graphed versus time for each subject to evaluate what function of time best describes the data. The mixed effects framework is robust with respect to drop-out and missing data, unless the drop-out mechanism or cause of missing is informative. We will use pattern-mixture models to assess if there is bias due to drop out or missing data. As described by Hedeker and Gibbons, these mixed models allow us to assess whether important estimates are dependent on missing data patterns and provide overall estimates of effects by averaging over the various missing-data patterns. In addition, we will consider the extension of the Pattern-Mixture models as described by Guo et al which includes the incorporation of random effects in the Pattern mixture model, allowing subject-to-subject heterogeneity.

Missing data values will be minimized by intensive training of interviewers in techniques of clarifying answers and checking questionnaires while participants are on-site. When missing values are identified, we will employ several approaches. If possible, participants will be rescheduled for missed assessments. Missing data will be examined to assess randomness. The pattern of missing data will be examined according to the procedure recommended by Little and Rubin which includes comparing group differences in the primary outcomes of subjects with versus without missing data. The Mixed effects model allows inclusion of subjects with missing data or those who terminated the study early, without relying on data imputation procedures.

**Hypothesis 1a)** PTSD symptom severity. Dependent variables: CAPS-V and PCL-5.

**Hypothesis 1b)** Functional impairment. Dependent variables: HVLTR, WAIS-IV (Digit Span subtest), DKEFS (Trails subtest), and COWAT (Verbal Fluency).

Independent variables: Treatment group (2 levels, CABA and TAU), & Time (3 levels, Weeks 0, 7, and 14). Statistical Analysis: We will analyze data on all randomized subjects in whom we have a baseline assessment and at least one post-baseline evaluation by Mixed effects model methods. Preliminary inspection of data will determine whether the outcome is nearly normal, or whether an appropriate transformation is required, or whether a generalized linear mixed model should be considered. The mixed effects model method provides an estimate of the individual variability around the population trend, the variability of the individual intercepts (baseline values) and slopes (changes across time), and the correlation between them. A fully saturated treatment by time model will be utilized for inference. Covariance structure will be chosen based on Akaike's Information Criterion (AIC). Random group level treatment effects will also be evaluated for importance based on the model AIC. This allows for any group level effects to be incorporated into the model. Denominator degrees of freedom will be calculated using the Kenward-Roger small sample correction. The design is a 2 (sites) X 2 (CABA vs TAU) X 3 (baseline, 7, and 14 weeks). The interaction of Site and Treatment X Site will be included and tested as

"nuisance parameters". However, we do not anticipate any Treatment by Site or Site effects with the balanced design (equal numbers at each site in each group), our standard training procedure of both sites and standard operating procedure used by both sites. In any case, the analysis procedures will include site and site interaction effects to avoid allowing site effects to bias treatment comparisons. If we detect any imbalances between the treatment groups within each site, we will follow the primary analyses above with subsequent analyses considering the imbalances to verify that the conclusions are not affected by imbalances. Analyses will be conducted within and across nested levels of the study design; this will involve within-subject analyses (comparison of occasions of measurement nested within an individual), as well as between-subject analyses (comparison of the CABA and TAU groups, comparison of groups within a site, comparison of sites, etc). Any treatment group comparison can be adjusted for subject-specific characteristics and adjustments for changes in these characteristics over the course of the study can be incorporated into single-subject analyses. All comparisons described in this section can be effectively analyzed using PROC MIXED in SAS statistical software. Based on our ongoing studies, we expect a drop-out rate of <15% after baseline assessment but prior to first post-baseline evaluation. The drop-out rate is taken into account in power analyses, see above.

**Hypothesis 2a)** Patient-centered outcomes. Dependent variables: BDI-II, NSI, and SLS. Independent variables: Treatment group (2 levels, CABA and TAU), and Time (3 levels, Weeks 0,7,14). Statistical Analysis: Data will be analyzed similar to hypotheses 1a and 1b.

**Hypothesis 2b)** Treatment satisfaction. Dependent variables: CSQ. Independent variables: Treatment group (2 levels, CABA and TAU). Statistical Analysis: Hypothesis 2b will be tested using Analysis of Variance, comparing the two groups on the treatment credibility and satisfaction (CSQ).

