### 5.7 Withdrawal of Subjects

Should any findings arise during assessment study visits which might affect the participant’s health or welfare, the study team will address those findings directly with participants during the assessment study visit within which the issues are discovered. The study team will use CPRS to identify the participant’s health care providers as well as communicate the findings with those providers and follow-up via telephone as needed.

The co-PIs will recommend termination of participation, provide appropriate referrals, and engage in follow-up if substantial decline in functioning is observed at any assessment study visit for all participants and/or treatment visits for those assigned to the CABA treatment intervention. Participation in this study therefore, will be terminated at the discretion of study personnel (with final determination by co-PI’s), based upon clinical observations and judgments regarding the safety of continued participation to the patient’s physical and/or psychological health and well-being. Additionally, if participants fail to comply with important instructions that are part of the approved study protocol, such as actively abusing substances, participation will be terminated without consent.

Although the proposed study poses no serious risks to participants, participants may notify research personnel about pre-existing mental health issues that have not been previously identified by other VA providers. Therefore, participants will be referred to the VA’s Mental Health Division for further

assessment and/or treatment if a previously undiagnosed psychiatric disorder is identified. We will inform participants of this procedure as part of the informed consent process and participants must agree to this procedure to be eligible to participate in the study. This ensures that we can adequately manage any pre-existing clinical issues that become apparent through subject evaluation.

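### Participants terminated before week 14 for decline short of inpatient care can be absent from both measures that feed the six-monthly suspension rule

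*Combined protocol and SAP*

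**What the plan says.** Section 5.6 (Data Safety Monitoring) states that "Safety monitoring analyses will occur every six months from study inception through completion". The statistician receives a data set with masked group labels containing "in-progress data safety variables including CAPS scores and any serious adverse events", of which four kinds are listed. The only listed event about functioning is "a decline in global daily functioning indicating that inpatient mental health services are required for stabilization". The other three are imminent risk of harm, onset of psychotic or manic symptoms, and interfering medical illness. The CIRB is consulted about possible suspension if "either group of participants is experiencing, on average, an increase in CAPS scores of 12 or more points", or if either group has significantly more SAEs, judged by t-test at p<.01 and/or d of .8 or more.

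Section 5.7 (Withdrawal of Subjects) has the co-PIs "recommend termination of participation, provide appropriate referrals, and engage in follow-up if substantial decline in functioning is observed at any assessment study visit". This applies to both arms; in CABA, decline noticed at a treatment visit counts as well. It sets no inpatient threshold. Potential Risks and Protection Against Risk, both within section 5.1, contain similar termination provisions. Section 5.7 then lets participants who choose to withdraw continue the assessments voluntarily. It says nothing on this point about participants whom the co-PIs terminate.

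Table 3 marks CAPS-V at week 0 and week 14. PCL-5 and BDI-II are marked at weeks 0, 7 and 14.

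**The concern.** A safety mean is informative only if the people who got worse are in it. Here, worsening can itself end participation before the only post-baseline CAPS, and the SAE definition of functional decline is set higher than the reason for termination. The missing scores would then depend on the harm being monitored. The loss could also differ by arm, since CABA participants have more occasions on which decline can be noticed and acted on. At stake is whether a six-monthly review that does not trigger can be taken as reassurance. The question is which data feed the rule, not how large its thresholds are.

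**Working it through.** **Tracing one participant.** The plan offers no figure to reproduce, so the provisions are set side by side for a participant terminated in week 9, say, for decline not requiring admission.

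| Question | Source | Answer |
|---|---|---|
| Post-baseline CAPS scheduled by then? | Table 3; section 5.5 gives questionnaires only at mid-treatment | No |
| Listed SAE on functioning met? | Section 5.6 | No, inpatient level required |
| Other listed SAE met? | Section 5.6 | Only if imminent risk, psychosis or mania, or interfering illness |
| Week-14 CAPS sought after termination? | Section 5.7 | Not stated |
| Termination named in the data set? | Section 5.6 | No |
| PCL-5 and BDI-II named in the data set? | Section 5.6 | No, although both are collected at week 7 |

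**Effect on the CAPS limb.** Let f be the share of an arm removed, D their mean CAPS change and m the mean change in the rest. The full-arm mean is (1-f)m + fD, while the mean seen by the rule is m. Take m = 54.7 - 72.7 = -18.0 (BA arm of the earlier trial, Table 1) and assume D = +30:
- f = 10%: seen -18.0; full arm 0.9(-18) + 0.1(30) = -13.2.
- f = 20%: seen -18.0; full arm 0.8(-18) + 0.2(30) = -8.4.
- To reach +12: f = (12 + 18)/(30 + 18) = 62.5%, or 60 of 96. With m = 0: f = 12/30 = 40%, or 39 of 96.

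The missing scores flatter the arm, but at these rates they do not change whether this limb fires. The Table 1 scores may not be on the same scale as CAPS-V.

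**Effect of counting terminations.** Two-sample t-test on 0/1 indicators, as section 5.6 uses for SAEs, with 96 per arm (section 5.2). All counts are assumed.

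| Terminations | t-test p | d |
|---|---|---|
| 7 v 0 | .0069 | 0.39 |
| 11 v 2 | .0096 | 0.38 |
| 12 v 2 | .0053 (Fisher .010) | 0.41 |

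For 12 v 2, d = (12/96 - 2/96)/0.256 = 0.104/0.256 = 0.41. The p<.01 criterion is met in each row. The d criterion is not: against 0 it needs 24 of 96. With fewer participants, p<.01 against 0 needs 6 of 24 or 7 of 48.

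**Timing.** Section 5.6 gives 6 months of start-up and full enrolment by month 39. Assuming even enrolment over the 33 months between, the rate is 192/33 = 5.82 per month. Fourteen weeks is 3.22 months and seven weeks is 1.61 months. At month 12, ignoring drop-out:
- enrolled: 6 x 5.82 = 34.9;
- reached week 7: 34.9 - 1.61 x 5.82 = 25.5;
- reached week 14: 34.9 - 3.22 x 5.82 = 16.2.

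About 19 (3.22 x 5.82 = 18.7) are between baseline and week 14 at each look from month 12 to month 36. The figure is 0 at month 6, about 1 at month 42 and 0 at month 48.

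**The case against.** There are real safeguards. The listed SAEs are introduced as examples, so others may be reported, and the three items not about functioning can catch some declines that need no admission. Termination may occur at the week-14 assessment, where a CAPS is scheduled. Section 5.1 promises continued contact with all participants, and the termination provisions mention follow-up. The co-PIs review all adverse events quarterly, and they both decide terminations and notify the CIRB. So a reader might infer that every participant terminated for decline falls out of both limbs, or that the review cannot see such harm. The documents do not support either statement.

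Nor do they support reading section 5.7 as barring assessments after termination; it is silent. Describing CAPS as in-progress need not conflict with Table 3, since it can simply mean data accruing while the trial runs.

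The 12 v 2 example is not a forecast. Twelve of 96 is 12.5% for decline alone, against 12.3% drop-out of all kinds in the earlier BA trial (section 5.6). The plan's 15% drop-out is also all-cause. The outcome analysis places it before the first post-baseline evaluation, so week-7 questionnaires would not recover those people.

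Finally, a simple between-arm test of all terminations would be biased by ascertainment, because decline can be seen at treatment visits in CABA only.

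All of this stands, and it narrows the point without removing it. The quarterly review has no stated group comparison or trigger, no provision says that a termination is logged as an adverse event, and the promised follow-up does not specify a CAPS.

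**Conclusion.** The point holds for a defined group: participants terminated by the co-PIs before week 14, for decline short of inpatient care, who meet no other SAE item. They have no scheduled post-baseline CAPS, match no listed SAE and are not otherwise named in the six-monthly data set. The CAPS mean behind the suspension rule can therefore be taken over those not removed for worsening.

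The size of the problem is unknown, because no termination rate is given. A reader might infer that the missing CAPS scores would have fired the 12-point limb. Under the assumed 30-point worsening they would not at 10% or 20% removed. What can reach the rule's own criterion is a count of terminations, for example 7 of 96 against 0. That rests on assumed counts and, if treatment-visit declines are included, on unequal observation. This is an inexpensive improvement to safety reporting, not evidence that the monitoring plan fails.

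**What to change.** In the Data Safety Monitoring paragraph of section 5.6, add to each six-monthly data set, by coded arm:

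1. The number of participants terminated for decline, with the reason and whether the decline was seen at an assessment or a treatment visit. Show all of them descriptively, but limit any between-arm test to declines seen at the assessment visits common to both arms. That test will miss CABA participants already removed after a treatment visit, so the full count should stand beside it.
2. PCL-5 and BDI-II change at weeks 7 and 14.
3. Next to each CAPS mean, the number of randomised participants who are past week 14, or terminated, with no post-baseline CAPS.

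Reconcile sections 5.6 and 5.7 on how decline is recorded for safety review, and state whether the week-14 assessment is still sought, voluntarily, from terminated participants. No clinical criterion needs to change.

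The cost is one revised paragraph, a sentence in section 5.7 and a few more columns in an existing transfer. No new instrument is needed, and PCL-5 and BDI-II are already collected in both arms. The downside is an occasional extra consultation with the CIRB.
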